#### **6.6.4. Missing End of Treatment Date**

For patients without a full end of treatment date (i.e., missing day, month, or year), the last study drug dispensation date will be used as the end of treatment date for purposes of analysis.

## 7. STUDY POPULATION

Data are summarized for the safety population (Section 6.3.1)

### 7.1. Subject Disposition

A disposition summary includes the number and percentage of patients in the following categories:

- Patients with prior participation in 402-C-1603 phase 2
- Patients with prior participation in 402-C-1603 phase 3 and randomized to placebo
- Patients with prior participation in 402-C-1603 phase 3 and randomized to bardoxolone methyl
- Patients with prior participation in 402-C-1808 phase 3 and randomized to placebo
- Patients with prior participation in 402-C-1808 phase 3 and randomized to bardoxolone methyl
- Patients completed study when the study was terminated
- Continuing (or complete) treatment
- Terminate early from the treatment
  - Reason for terminating treatment
  - Terminated early from the treatment due to COVID-19
- Continuing (or complete) study
- Terminate early from the study
  - Reason for terminating study
  - Terminated early from the study due to COVID-19
  - Study week at study termination
  - Terminated prior to SDT
  - Terminated after SDT

Results will be summarized by analysis population (Section 6.3). A listing of disposition is provided for all patients.

### 7.2. Screen Failures

Lab assessments from the qualifying study will be used for EAGLE eligibility and maximum treatment dose assignment (Week 100 for CARDINAL or FALCON protocol versions 1 through 5, and Week 108 [B] for FALCON versions 6 and newer) if those assessments were done  $\leq 8$  weeks before Day 1. In the event that the eligibility lab assessments were obtained  $> 8$  weeks before the planned EAGLE Day 1 visit, a screening visit will be required for EAGLE enrollment. Subjects who previously were ineligible due to previous eGFR requirements may be rescreened once.

Screen failures are not summarized.

### 7.3. Protocol Deviation

Protocol deviations for major protocol deviations and protocol deviations related to COVID-19 are summarized.

Major protocol deviations include but not limited to:

- Protocol deviations for patients who entered the study even though they did not satisfy all entry criteria.
- Patients who received an incorrect dose.

All protocol deviations are listed.

### 7.4. Demographic and Baseline Characteristics

Summaries of demographic and other baseline characteristic data are presented by treatment analysis group (Section 4.5) for all the safety populations.

The demographic and other baseline characteristics include:

- Age, Age category at the date of informed consent ( $< 18, \geq 18$ )
- Race
- Ethnicity: Non-Hispanic/Latino; Hispanic/Latino
- Sex: (female; male)
- Weight (kg), body mass index ( $\text{kg}/\text{m}^2$ )
- Geographic location: United States; Other
- Diastolic and systolic blood pressure (mmHg), Heart rate (bpm)
- SCr, eGFR, eGFR categorical status ( $< 60, \geq 60 \text{ mL}/\text{min}/1.73 \text{ m}^2$ )
- ACR (geometric mean), ACR categorical status ( $< 30 \text{ mg}/\text{g}; \leq 300 \text{ mg}/\text{g}; > 300 \text{ mg}/\text{g}; > 1000 \text{ mg}/\text{g}$ ),
- Angiotensin converting enzyme-inhibitor treatment and/or Angiotensin II receptor blocker (yes/no)
- Genetic subtype: X-linked Alport syndrome; Non-X-linked Alport syndrome (for Alport patients only)
- Chronic kidney disease etiology: Alport syndrome; autosomal dominant polycystic kidney disease (ADPKD)
- Family history of ADPKD (for ADPKD patients only)
- Use of tolvaptan (for ADPKD patients only)
  - Currently using tolvaptan
  - Previously used tolvaptan
  - Never received tolvaptan

- Prior study: 402-C-1603 phase 2, 402-C-1603 phase 3, 402-C-1808

## **7.5. Listing of Subject Inclusion and Exclusion Criteria**

A listing of enrolled patients who did not meet inclusion or exclusion criteria is generated.

## **7.6. Medical History**

Medical history is summarized by treatment analysis group (Section 4.5). If medical history values are not recorded in 402-C-1803, then medical history values recorded at the 402-C-1603/402-C-1808 screening visit are used for analysis. Medical history is coded using the Medical Dictionary for Regulatory Activities (MedDRA). Medical history items are summarized by MedDRA System Organ Class (SOC) and preferred term (PT). Patient listings are also provided.

## 8. SAFETY AND TOLERABILITY

Safety and tolerability are evaluated by AEs, SAEs, clinical laboratory test results, body weight, vital signs, and physical examination. All analyses of the safety data are performed using the safety analysis set. Descriptive statistics are presented by treatment analysis group (Section 4.5) assignment in the all analysis populations. No formal statistical testing is performed for safety analyses. Any results not included in summaries based on analysis visit window definitions are presented in data listings.

### 8.1. Adverse Event Preferred Term and Body/Organ System Summary Tables

Adverse events are summarized by treatment as defined by the safety analysis set. General considerations for AE summaries and calculations are:

- Multiple events by PT and SOC are counted once only per patient for summaries of AE incidence.
- For summaries of AE incidence by severity, only the most severe event is counted per patient.
- For summaries of AE incidence by relationship, only the most related event is counted per patient.
- An AE with a missing resolution date or incomplete date that is not identified as continuing is assumed to be continuing and no duration is calculated.
- Only TEAEs are included in summaries.

Adverse events are coded using MedDRA version 21.1. In MedDRA, each verbatim term is mapped to a PT and high-level term, which is then mapped to an SOC. Tables and listings will present data at the SOC and PT level.

Treatment emergent adverse events (TEAEs) are events that either:

- Have a date of onset on or after the date of the first dose in the 402-C-1803 study and not more than 30 days after the date of the last dose of study drug in the 402-C-1803 study, or
- Have no recorded date of onset with a stop date after the first dose of study drug, or
- Have no recorded date of onset or stop date

Adverse events with a date of onset in a prior study that continued during the 402-C-1803 study are not considered TEAEs.

In addition, AEs that occurred >30 days after the date of last dose of study drug are summarized as late-onset AEs. These are AEs that had a date of onset more than 30 days after the date of the last dose of study drug in 402-C-1803 study.

The investigator grades the severity of the AEs as mild, moderate, or severe as defined in the study protocol Section 11.5. The investigators graded association or relatedness to the study medication according to criteria specified in Section 11.4 of the study protocol.

As defined in the protocol, an SAE is an AE that results in any of the following:

- Death;
- A life-threatening adverse drug experience;
- Patient reaches ESKD (defined as the initiation of maintenance dialysis for 12 weeks or more or kidney transplant)
- Inpatient hospitalization or prolongation of existing hospitalization;
- Results in persistent or significant incapacity or substantial disruption of the ability to conduct normal life functions;
- Results in a congenital anomaly or birth defect in an offspring of a patient taking study drug;
- Is an important medical event.

### **8.1.1. Missing and Partial AE Onset Dates**

Rules for handling missing or partial AE onset dates are included in Section [6.6.3](#).

### **8.1.2. Summaries of Adverse Events**

For each treatment analysis group, SOC, and PT, the number and percentage of patients reporting an event is calculated. In summary tables, SOC is presented alphabetically and events within SOC are presented by decreasing frequency count.

Summary tables (number and percentage of patients and events) of AEs (by SOC and PT) are provided by treatment analysis group as follows:

- All TEAEs
- All treatment-emergent related AEs (definitely, probably, or possibly related)
- All TEAEs by severity
- All treatment-emergent SAEs (including deaths)
- All related treatment-emergent SAEs (including deaths)
- All TEAEs leading to permanent discontinuation of study drug

Listings are provided showing:

- All AEs
- SAEs (including deaths)
- AEs leading to permanent discontinuation of study drug

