**Diagnosis and main criteria for exclusion (see protocol Section 8.2):**

1. Participation in other investigational clinical studies involving interventional products being tested or used in a way different from the approved form or when used for an unapproved indication;
2. Patients who have an ongoing serious adverse event from a clinical study that is assessed by the investigator as related to bardoxolone methyl.
3. Unwilling to practice acceptable methods of birth control (both males who have partners of childbearing potential and females of childbearing potential) while screening, taking study drug and 30 days after the last study drug dose.
4. Women who are pregnant or breastfeeding.
5. Patient is, in the opinion of the investigator, unable to comply with the requirements of the study protocol or is unsuitable for the study for any reason.
6. Known hypersensitivity to any component of the study drug.

**Test product, dose and mode of administration:** Bardoxolone methyl will be administered at oral doses 5, 10, 20, or 30 mg. Each dose of study drug is administered at approximately the same time each day, preferably in the morning.

**Duration of treatment:** Until bardoxolone methyl is available through commercial channels or until patient withdrawal or study termination, whichever is sooner.

**Reference therapy, dose and mode of administration:** No reference therapy

**Criteria for evaluation (see protocol Section 6.2):** Safety: Results of physical examination, laboratory results, ACR, vital sign measurements, weight, AEs, and SAEs.

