**Statistical methods:**

Sample size: The aim of this long-term extended access study is primarily to provide continuing bardoxolone methyl treatment to patients and to assess long-term safety and tolerability, hence no single primary variable has been identified. Patient numbers will be determined by those who are participating (or who have previously participated) in a qualifying clinical study with bardoxolone methyl and meet eligibility requirements.

Primary analysis of safety: As the extension is an open-label design with no comparator group, all statistical analyses will be descriptive. The summary tables will be presented for the overall group of patients and split by previous treatment groups (ie, bardoxolone methyl or placebo) in prior bardoxolone methyl clinical studies.

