### **4.5. Treatment Analysis Group Assignment**

The treatment analysis groups for the 402-C-1803 study consist of:

1. Placebo → Bardoxolone (Bard): placebo-bardoxolone methyl patients (patients previously randomized to placebo in 402-C-1603 Phase 3 or 402-C-1808 who started receiving bardoxolone methyl in 402-C-1803),
2. Bard → Bard: bardoxolone methyl patients (patients previously randomized to bardoxolone methyl in 402-C-1603 Phase 3 or 402-C-1808 who started receiving bardoxolone methyl in 402-C-1803). Data from 402-C-1603 or 402-C-1808 must be unblinded to be included in either treatment analysis group.

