### **6.2. General Post Text Summary Table and Individual Subject Data Listing Format Considerations**

Unless otherwise specified, descriptive statistics for continuous variables include the number of patients with data (N), mean, SD, median, minimum, and maximum. The same number of decimal places as in the observed value are presented when reporting minimum and maximum; 1 more decimal place than in the observed value is presented when reporting mean and quartiles; and 2 more decimal places than in the observed value is presented when reporting SD.

Categorical (qualitative) data are presented using frequency counts and percentages. All percentages are rounded to 1 decimal place, unless otherwise specified. Percentages equal to 100 are presented as 100% and no percentages are presented for zero frequencies. Where individual variable values are missing, summaries of categorical data are based on reduced denominators (ie, only patients with available data are included in the denominators). For summaries of AEs and concomitant medications, the percentages are based on the number of patients who received study drug within each summary group.

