### **6.3.3. 402-C-1808 to 402-C-1803 Safety Population**

The 402-C-1808 to 402-C-1803 safety population includes all patients previously enrolled in 402-C-1808 study who received at least 1 dose of bardoxolone methyl in 402-C-1803 study.

Subgroup analyses will not be conducted due to termination of the bardoxolone methyl program. However, summaries based on the parent studies (402-C-1808 and 402-C-1603) will be provided along with a pooled analysis.

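### SAEs, deaths and AEs leading to discontinuation are tabulated as percentages with no stated follow-up time; adding patient-years and fixed-time cumulative incidence would be a cheap, optional improvement

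*SAP*

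**What the plan says.** - **AE tables.** SAP 8.1.2 states that "the number and percentage of patients reporting an event is calculated" for each treatment analysis group, system organ class and preferred term, and its tables also give numbers of events. They cover treatment-emergent SAEs (deaths included) and TEAEs leading to permanent discontinuation. SAP 6.2 fixes the denominator: "the percentages are based on the number of patients who received study drug within each summary group".
- **Groupings.** SAP 8: "Descriptive statistics are presented by treatment analysis group (Section 4.5) assignment in the all analysis populations". The SAP technical summary: "The summary tables will be presented for the overall group of patients and split by previous treatment groups". SAP 6.3.3 adds that "summaries based on the parent studies (402-C-1808 and 402-C-1603) will be provided along with a pooled analysis".
- **Treatment duration.** "Until bardoxolone methyl is available through commercial channels or until patient withdrawal or study termination, whichever is sooner" (SAP technical summary).
- **Repeated reporting.** SAP 2 and 5.1 re-run the full set of outputs at successive database locks.
- **Time and exposure.** SAP 8.2 summarises days of exposure as a variable in its own right. SAP 6.5.2 defines days since first dose for listings. The one AE timing split, in SAP 8.1, is for events starting more than 30 days after the last dose.
- **Kidney outcomes.** SAP 8.4.2.2 plans proportions of patients for ESKD, eGFR decline, eGFR below 15 and their composite, and says that the frequency analyses cover all visits, without naming a denominator.

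**The concern.** When patients are followed for very different lengths of time, the percentage who ever had an SAE depends on the hazard and on how long they were watched. Two parent-study columns can then differ although the risk is the same, and one column can rise from one database lock to the next only because time has passed. That matters most for events that keep accumulating: SAEs, deaths, discontinuation AEs and kidney events. It matters little for effects confined to the first weeks, such as the early fluid-overload risk described in Protocol 5.1.2.1. For a long-term safety study, the natural questions are how often per year on drug and what proportion by a given time. No planned AE table answers either.

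**Working it through.** The plan gives no event rate, sample size or follow-up figure, so there is none to reproduce.

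**1. Calendar ceilings on follow-up.** Inputs: first patient first visit in March 2019, day not given (SAP technical summary); Version 3, dated 30 June 2020, whose change document adds FALCON as a qualifying study (used here only to date FALCON entry); Version 4, dated 9 November 2022, and the termination notice, dated 10 May 2023 (both SAP 2). Formula: (10 May 2023 − earliest entry) / 365.25.

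- From 1 to 31 March 2019: 1531 to 1501 days = 4.19 to 4.11 years (mid-March 4.15).
- From 30 June 2020: 1044 days = 2.86 years.
- From 9 November 2022: 182 days = 0.50 years.

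Actual entry and site approval dates are not in the documents, so real follow-up may be shorter.

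**2. What equal risk would look like.** Assume a constant first-event rate r, which is not a document figure. With everyone at the ceiling T, the crude proportion is 1 − exp(−rT). For r = 0.10 per year:

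- T = 0.50: 4.9%
- T = 2.86: 24.9%
- T = 4.15: 34.0%, a ratio of 1.37 to the 2.86-year figure

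At r = 0.02 the last two are 5.6% and 8.0% (ratio 1.43). At r = 0.20 they are about 44% and 56% (ratio about 1.3).

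If entry is instead uniform from each start date to the notice, the proportion is 1 − (1 − exp(−rT))/(rT). For r = 0.10 this gives 13.0% at T = 2.86 and 18.2% at T = 4.15, ratio 1.39.

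**3. Sensitivity to the CARDINAL start.** The prior-bardoxolone group is defined as "patients previously randomized to bardoxolone methyl in 402-C-1603 Phase 3 or 402-C-1808 who started receiving bardoxolone methyl in 402-C-1803", so CARDINAL Phase 2 patients fall in neither treatment analysis group. If the earliest entrants were Phase 2 patients, by-group CARDINAL follow-up would start later. With an assumed start in March 2020, T = 3.11 to 3.19 years. At r = 0.10 that gives 26.7% to 27.3% against 24.9%, ratio 1.07 to 1.10.

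**4. Successive locks.** The first lock was 22 November 2019 (SAP 2), 236 to 266 days (0.65 to 0.73 years) after first entry. At r = 0.10 a first entrant's cumulative risk is 6.3% to 7.0% at that lock and 33.7% to 34.2% at the notice, with no change in hazard.

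**5. What can be rebuilt from planned tables.** N times mean exposure (SAP 8.2) gives total patient-days, and SAP 8.1.2 gives event counts. Their quotient approximates a total-event rate on drug. It is not a first-event rate, it omits the 30 days after last dose that count towards TEAEs, and it gives no cumulative incidence. First-event timing could be recovered only from listings.

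**6. Why a rate alone is not enough.** Suppose 20% of patients have an event around Week 4 (0.077 years) and nobody has one later. The rate per 100 patient-years is 20 / (0.2 × 0.077 + 0.8 × T): about 48, 8.7 and 6.0 at T = 0.5, 2.86 and 4.15. The risk is identical and the rate falls eightfold, so rates need cumulative incidence beside them.

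**The case against.** The study is descriptive. Its endpoint is frequency, intensity and relationship of AEs, and n (%) with event counts delivers that. Exposure is tabulated, so a careful reader can form an approximate rate. Parent-study tables are summaries rather than a planned contrast, and Alport syndrome and ADPKD differ in ways that person-time cannot remove. The programme has ended and subgroup analyses were dropped. All of this stands. It caps the point at a presentation improvement, but it does not supply a first-event rate or a percentage tied to a time.

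Four stronger readings are tempting and are not supported:

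- **That the comparison of prior placebo with prior bardoxolone is distorted.** Nothing in the documents suggests that follow-up differs between those groups.
- **That follow-up in fact varied about eightfold.** The figures are ceilings from version dates, and nothing shows that anyone entered after Version 4.
- **That nothing links events to time.** Event counts, the exposure summary, study week at termination and the listings do so in part. For kidney outcomes, SAP 8.4.2.2 may intend a table by visit.
- **That patients reaching ESKD drop out of the kidney denominators.** Protocol 8.5 makes them leave the study, and the SAP 6.2 default for other categorical data is that "only patients with available data are included in the denominators". But SAP 8.4.2.2 defines patient-level outcomes, and its reference to all visits may mean only that all visits contribute data. This is one reading of unclear text.

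**Conclusion.** The point holds as an optional improvement. Planned AE tables for events that accumulate give percentages of dosed patients, plus event counts, with no person-time denominator and no fixed time since first dose. With open-ended treatment and staggered entry, the pooled, parent-study and successive-lock percentages mix risk with time on study.

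The size is unknown. The ratio of about 1.4 between parent studies assumes a constant, equal hazard, the same entry pattern in both parent studies, and follow-up set by the document dates. It shrinks to 1.07–1.10 under one plausible change in CARDINAL entry. No planned inference is shown to be wrong.

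**What to change.** **SAP 8.1.2.** Keep n (%) and event counts. For treatment-emergent SAEs, deaths and TEAEs leading to discontinuation only, by treatment analysis group, parent study and pooled, add:

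1. patient-years at risk;
2. first-event rate per 100 patient-years with 95% CI;
3. cumulative incidence with number at risk at fixed times since first EAGLE dose, for example Weeks 24, 48 and 96.

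Time at risk should match the numerator's window, the SAP 8.1 TEAE definition: first dose to the earliest of first event, last dose plus 30 days, death, or last contact or data cut-off. Protocol 9.9.12 can end AE collection sooner, at the End of Study visit; the last-contact limit covers that.

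Flag patients whose last dose is set to the last dispensation date (SAP 6.6.4 and 8.2). With 24-weekly dispensing, up to 168 days (168/365.25 = 0.46 years) per affected patient can be missed.

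**SAP 8.4.2.2.** Add cumulative incidence of the composite and its components within the windows already set there, with death as a competing event except in the sensitivity analysis that counts it.

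**Separate clarification in 8.4.2.2.** State whether covering all visits means a by-visit table. If so, count events cumulatively over all dosed patients, so that those who leave at ESKD stay in the denominator.

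**Cost.** SAP wording and some programming, from dates already collected. Rates assume a roughly constant hazard, so say that they are read beside n (%) and cumulative incidence. Leaving at ESKD may make censoring for SAEs and deaths informative, so report how many patients were censored for that reason.

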7.3.1. Dose Escalation

Adult patients (≥ 18 years of age) receiving bardoxolone methyl will start with once-daily dosing at 5 mg and will dose-escalate to 10 mg at Week 2, to 20 mg at Week 4, and then to 30 mg at Week 6 (only if eligibility ACR > 300 mg/g) unless contraindicated clinically and approved by the medical monitor. Patients from the CARDINAL study under the age of 18 at the time of consent for participation in the EAGLE study will start dosing at 5 mg every other day during the first week (from Day 1 through the Week 1 visit) and begin once-daily dosing with 5 mg during the second week of the study (following the Week 1 visit through the Week 2 visit), and then continue with once-daily dosing following the same aforementioned dose-titration scheme based on eligibility ACR at Weeks 2, 4, and 6. Patients from the FALCON study under the age of 18 at the time of consent for participation in the EAGLE study will follow the adult dose titration schedule. Dose escalation may proceed slowly if the patient experiences early elevation in ALT/AST over ULN eg, at Week 2 (See Section 9.1.2). The dosing objective is to titrate patients to the maximum dose determined by eligibility ACR and maintain the maximum dose after initial dose-titration. The investigator should discuss any reason for not dose-escalating at Weeks 2, 4, or 6 with the medical monitor.

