7.3.2. Dose De-Escalation and Re-Escalation

The investigator may choose to decrease the patient's dose to the prior dose (eg, 20 mg to 10 mg, or 10 mg to 5 mg), if clinically indicated. Dose de-escalation may occur more than once, but the minimum dose permitted is 5 mg. Reasons for dose de-escalation should be discussed with the medical monitor prior to changing the dose and must be documented. After dose de-escalation, patients must return for an unscheduled, in-clinic visit within 4 weeks (± 3 days) to perform the assessments detailed in Section 9.6.

If a patient's dose has been reduced, dose re-escalation back to a higher dose is permitted to meet the dosing objective. However, patients who dose re-escalate must have a telephone call 1 week (± 2 days) after dose re-escalation and an unscheduled, in-clinic visit 2 weeks (± 3 days) after dose re-escalation to perform the assessments detailed in Section 9.6.

Patients who had a delayed initial dose-escalation should also have a telephone call 1 week (± 2 days) after each dose escalation and an in-clinic visit 2 weeks (± 3 days) after dose escalation to perform the assessments detailed in Section 9.6. If these timepoints no longer coincide with scheduled study visits, unscheduled phone calls and in-clinic visits should occur. These do not replace the regularly scheduled study visits; they should be performed as well.

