11.6. Recording Adverse Events

All conditions present prior to the administration of the first dose of study drug (Day 1) should be documented as adverse events in the prior trial with bardoxolone methyl. Any new event/condition that starts during the gap between prior qualifying study and Day 1 of EAGLE should be recorded as medical history in EAGLE. AEs should be reported from the time of the first dose through 30 days after the last dose or the End of Study visit, whichever is earlier.

Information to be collected includes type of event, date of onset, date of resolution, investigator-specified assessment of severity and relationship to study drug, seriousness, as well as any action taken.

For guidance on how to handle AEs that change in severity (eg, worsening or improving) see the eCRF Completion Guidelines. All drug-related (possibly, probably, or definitely related, see Section 11.4) AEs and clinically significant abnormal laboratory test results reported or observed during the study must be followed to resolution (either return to baseline, within normal limits, or stabilization). All non-drug related AEs or clinically significant abnormal laboratory results will be followed through the 30 days after the last dose of study drug.

AEs resulting from concurrent illnesses, reactions to concurrent illnesses, reactions to concurrent medications, or progression of disease states must also be reported. Preexisting conditions (present before the start of the AE collection period) are considered concurrent medical conditions and should NOT be recorded as AEs. However, if the patient experiences a worsening or complication of such a concurrent condition, the worsening or complication should be recorded as an AE. Investigators should ensure that the AE term recorded captures the change in the condition (eg, “worsening of...”). Any improvement in condition should be documented per Section 9.9.7.

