5. DOSE MANAGEMENT

5.1. Dose De-escalation and Interruption for Missed Safety and Laboratory Assessments

If no scheduled in-clinic visit is completed and remote assessments/laboratory samples cannot be collected within the protocol allowed time window for that visit, the IP dose must be de-escalated to the previous dose within 6 days of the protocol visit window. For patients on 5 mg, the lowest dose, that dose may be maintained, and no de-escalation is required. All efforts should then be made to collect laboratory samples. However, if laboratory samples cannot be collected within 14 days from the date of dose de-escalation (for visits through Week 12) and within 28 days (for visits beyond Week 12), IP must be temporarily interrupted until safety lab values can be evaluated and it is deemed appropriate to restart. Appendix 1 Section 5.2 describes the procedure for resuming and dose-escalating IP following drug interruption.

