### **3. STUDY OBJECTIVES AND ENDPOINTS**

#### **3.1. Study Objectives**

##### **3.1.1. Primary Objective**

To provide continuing open-label treatment with bardoxolone methyl as part of this extended access program while collecting ongoing safety and tolerability data of bardoxolone methyl.

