## **8.2. Exposure and Compliance**

The duration of study drug exposure is defined as the number of days on treatment from the first dose of 402-C-1803 study drug until the last dose of study drug (last dose – first dose + 1). Study drug exposure is summarized by descriptive statistics. Summaries include the total dose (mg) received (based on the number of pills returned), study drug compliance, and duration (days) of

exposure during the study treatment period. In addition, a summary of the number and percentage of patients by dose (5 mg, 10 mg, 20 mg, 30 mg) and by visit window (Section 6.5.4) is generated. If a patient received more than one dose during a visit window, the duration of the longest dose exposure is used to calculate study drug dose during a given visit window.

Total number of doses dispensed and total dose (mg) dispensed is calculated from total number of kits (bottles) recorded on the Study Drug Dispensation electronic case report form (eCRF). Total number of doses received is calculated from information on the eCRF of Study Drug Return and Study Drug Dispensation, as the (total number of doses dispensed – total number of doses returned). Study drug compliance (%) is calculated as  $100 \times \text{total number of doses received} / \text{total number of study days of study participation}$ . For patients who remain on study treatment at the time of an interim or final data cut, the last kit dispensed date is considered the date of last dose. Any dispensation of drug after a subject has his or her end of treatment visit will not be used in any calculation.

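### The SAP plans no summary of adverse events leading to interruption or dose reduction, and no count of patients reaching and holding their assigned dose; the exposure tables cannot fill the gap

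*SAP*

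**What the plan says.** SAP 3.1.1 joins continued treatment to "collecting ongoing safety and tolerability data of bardoxolone methyl". SAP 8 then states how this is judged: "Safety and tolerability are evaluated by AEs, SAEs, clinical laboratory test results, body weight, vital signs, and physical examination". Dose modification is not named.

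SAP 8.1.2 plans six AE summaries: all TEAEs, related TEAEs, TEAEs by severity, treatment-emergent SAEs, related SAEs, and "All TEAEs leading to permanent discontinuation of study drug". The three listings are all AEs, SAEs, and AEs leading to permanent discontinuation.

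SAP 8.2 adds exposure duration, total dose, compliance, and a table of patients by dose level and visit window. When the dose changes within a window, "the duration of the longest dose exposure is used to calculate study drug dose during a given visit window". SAP 10.1 counts interruption, de-escalation and non-escalation, but only as COVID-19 impact.

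The protocol's dosing aim (7.3.1) is to "titrate patients to the maximum dose determined by eligibility ACR and maintain the maximum dose after initial dose-titration". De-escalation may be repeated and reversed (7.3.2): "Reasons for dose de-escalation should be discussed with the medical monitor prior to changing the dose and must be documented". Interruption has its own rules (7.3.3). For each AE, Protocol 11.6 requires, among other items, "relationship to study drug, seriousness, as well as any action taken".

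**The concern.** The protocol expects patients with intolerance to stay in the study on changed exposure. Section 9.8 offers dose reduction for tolerability problems. Temporary stopping is used for suspected fluid retention (9.1.1), for defined ALT/AST criteria (9.1.2) and for adolescent weight loss (9.1.4). Stepping down may be used for persistent nausea (9.1.8). Permanent discontinuation is the end of that sequence, yet it is the only step for which the SAP links AEs to dosing.

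Suppose a patient is interrupted several times for fluid or ALT and resumes each time. The patient appears in the AE and laboratory tables, but no summary shows that treatment had to be stopped. The report also could not say how many patients met the protocol's own dosing aim.

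**Working it through.** No sample size, power or event rate is at issue. The check is whether any other planned output could supply the missing link.

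**1. Outputs defined by effect on dosing.** In SAP 8.1.2 there is one table and one listing, both for permanent discontinuation. The all-AE listing might carry the action taken, but the SAP does not say so, and a listing gives no counts. Disposition (SAP 7.1) covers only those who terminate early.

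**2. Exposure duration (SAP 8.2).** Duration = last dose − first dose + 1. Days off drug between those dates are not subtracted.

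**3. Compliance and total dose (SAP 8.2).** Compliance = 100 × doses received / study days. It counts doses, not milligrams, so a step-down leaves it unchanged. An interruption lowers it, but so does a forgotten dose; Protocol 9.4 treats both as missed doses. Total milligrams fall with either kind of change, but also vary with the assigned maximum and with time in the study. Neither measure identifies an AE as the cause.

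**4. Dose by visit window (SAP 8.2 with Table 2).** The categories are 5, 10, 20 and 30 mg; there is none for interrupted. Coverage of study days is:
- Days 1 to 210: contiguous windows.
- Week 24 to Week 48: 308 − 210 − 1 = 97 days uncovered.
- Week 48 to Week 72, and between each later pair: 476 − 364 − 1 = 111 days uncovered.
- Each window from Week 48: 28 + 1 + 28 = 57 days. Share of each 168-day cycle covered: 57/168 = 33.9%; not covered: 111/168 = 66.1%.
- Cumulative to Day 364: (210 + 57)/364 = 267/364 = 73.4%.
- Cumulative to Day 700: (210 + 3 × 57)/700 = 381/700 = 54.4%.
- Cumulative to Day 1036: (210 + 5 × 57)/1036 = 495/1036 = 47.8%.

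A dose change that starts and ends in a gap is not shown.

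**5. The longest-dose rule inside a window.** As an illustration, assume one step-down with the rest of the window at full dose.
- 57-day window: a 28-day step-down leaves 57 − 28 = 29 days at full dose, so the table shows full dose.
- Week 24 window: 210 − 127 + 1 = 84 days. A 41-day step-down leaves 43 days at full dose, so the table again shows full dose.

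These durations are assumptions. The four-week limit in Protocol 7.3.2 times a return visit; it does not limit how long the lower dose is held.

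**6. Mixed causes in the dose rows.** The 20 mg row combines patients whose maximum is 20 mg with patients stepped down from 30 mg. Lower rows can also include reductions made for missed assessments, where under Protocol Appendix 1, Section 5.1 "the IP dose must be de-escalated to the previous dose within 6 days of the protocol visit window". SAP 10.1 counts COVID-19 de-escalations separately, but the dose-by-window table does not separate them.

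**The case against.** The strongest reply is that tolerability is already well covered. Every AE that led to a dose change is counted among all TEAEs, by severity and by relatedness. Liver events also have shift and threshold tables (SAP 8.4.2). Fluid is reflected in BNP above 200 pg/mL (8.4.2) and in weight gain of 2.3 kg or more (8.5.1). The primary endpoints (SAP 3.2.1) are AE frequency, intensity and relatedness plus changes from baseline, and none goes unanalysed. All of this stands, and it limits the point to the lost link with dosing.

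Second, the window gaps fall where least intolerance is expected. Protocol 5.1.2.1 to 5.1.2.3 and 9.1.8 place fluid events, transaminase peaks, muscle spasms and nausea mostly in the first weeks or two months, or soon after a dose increase. Windows are contiguous then, and between Day 2 and Day 70 they are 9 to 21 days long, so slow titration is largely visible. This stands for the early dose level. Even there, the table has no interrupted category and no tie to an AE.

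Third, development has been stopped (SAP 2) and subgroup analyses dropped (6.3.3). But the AE and exposure tables remain planned, so this is no reason to leave out the missing ones.

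A reader might infer that most intolerance goes unreported, or that the uncounted patients outnumber permanent AE discontinuations. The documents support neither: they give no rate of interruption, reduction or permanent discontinuation for this study. The 4% to 11% with transaminases above 3X ULN (Protocol 5.1.2.2) is not an interruption rate either, because Table 6 in Protocol 9.1.2 does not call for interruption on that finding alone.

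**Conclusion.** The point holds as an omission in reporting, and correcting it is a cheap improvement. The SAP plans no summary of TEAEs leading to interruption or dose reduction. Outside COVID-19 impact, it plans no count of patients interrupted, de-escalated, or reaching and holding their assigned maximum. The exposure outputs cannot stand in, for the reasons shown in the working.

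The size can be given only in study days: from Week 48, 111 of every 168 days lie outside the windows, and the longest-dose rule can hide shorter changes inside them. The number of patients affected is unknown. The omission biases no stated endpoint.

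The conclusion assumes that the outputs named in the SAP are the complete set. The remedy assumes that the action-taken field distinguishes interruption from reduction; Protocol 11.6 does not list its categories.

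**What to change.** In SAP 8.1.2, add two tables by SOC, PT and treatment analysis group: TEAEs leading to study drug interruption, and TEAEs leading to dose reduction. Build both from the action-taken field.

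In SAP 8.2, add one table within each assigned maximum (20 or 30 mg) giving the number and percentage of patients who:
- reached that maximum;
- were on it at last dose;
- were ever interrupted;
- were ever de-escalated.

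Split interruptions and de-escalations by reason (AE; COVID-19 or missed laboratory assessments; other) where the eCRF records it. Protocol 7.3.2 requires reasons for de-escalation to be documented but does not say that they enter the eCRF. If they do not, report the counts without the split and say so.

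The cost is a few extra tables, with no change to procedures or populations and, if the fields are as assumed, no new data collection. The tolerability figures may look less favourable.
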